3.3 Enrollment Procedures

To enter a patient, the investigator or study team will contact the CRS representative. All eligibility requirements must be reviewed prior to the patient entering the study. The following information must be provided to the CRS representative:

- 1) Completed and signed eligibility checklist.
- 2) All pages of the original signed informed consent forms (ICFs), including HIPAA form B.
- 3) Relevant source documents such as: subject medical history and physical exam; admission or discharge notes; diagnostic reports; pathologic confirmation of diagnosis by University of Miami pathologists (UM review) and relevant subject-specific communication.
- 4) To assure compliance with early stopping for toxicity, the monitor will inform the study team when the forth patient may be enrolled.

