5.2 Evaluations During Treatment

- High dose boost will be started on a Monday, Tuesday or Wednesday.
- Plasma and serum (up to 4 tubes) and urine (50 mL) will be collected for research (research fluids) at 24 hr post-LEAD RT and during the last week of RT.
- Weekly history and physical, evaluation of patient's ability to perform daily activities (Zubrod performance status; Karnovsky or ECOG performance status may be used to estimate Zubrod), and evaluation of toxicity.
- Blood (up to 4 tubes) will be drawn at RT completion during the last week of RT from a vein for the following tests:
 - Serum Testosterone.
 - Liver function tests (only if on ADT)
 - Complete cell counts
 - Lipid profile
- Quality of Life surveys will be administered during the last week of RT:
 - The Expanded Prostate Cancer Index Composite Questionnaire-SF12 (EPIC-SF12)
 - Memorial Anxiety Scale for Prostate Cancer patients (MAX-PC)
- International Prostate Symptom Index (IPSS) questionnaire during the last week of RT.

5.3 Post-treatment Evaluations (after RT) *Measurements and follow-up visits should occur ± 2 weeks up to the 3 month visit and ± 4 weeks for subsequent measurements/visits*

- History and physical, evaluation of patient's ability to perform daily activities (Zubrod performance status; Karnovsky or ECOG performance status may be used to estimate Zubrod), and evaluation of side effects at 6 weeks, 3 months, and then every 6 months for 5.25 years.
- Blood work (tubes of blood will be drawn at each follow-up as described below):
 - PSA at 6 weeks, 3 months and then every 6 months for 5.25 years.
 - Testosterone at 6 weeks, 3 months, and 9 months after radiotherapy. If testosterone remains abnormally low after ADT, tests will continue to be done at each follow-up visit.
 - BUN and creatinine to evaluate kidney function prior to MRIs at 3 months, 9 months and within 2 months prior to the 2-year prostate biopsy.
 - Liver function tests at 6 weeks and 3 months after radiotherapy (only at 3 months if not receiving ADT).
 - Complete blood counts at 3 months.
 - Lipid profile at 6 weeks, 3 months, 9 months, and within 2 months prior to the 2-year prostate biopsy.
- Plasma and serum (up to 4 tubes), and urine (50 mL) for research fluid tests will be obtained at 6 weeks, 3 months, 9 months and within 2 months prior to the 2-year prostate biopsy.

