9.1 Definitions

- *Feasibility*: The proportion of enrolled patients for whom LEAD RT dose can be successfully administered following MRI-guided planning.
- *Acute toxicity*: Grade 2 or higher treatment-related acute GU/GI toxicity occurring during treatment and within 30 days of completing treatment. The severity of the reactions to the treatment is scored according to the criteria outlined in Appendix II.
- *Late toxicity*: Delayed toxicities are usually related to urinary, rectal, and sexual function. The anticipated urinary and rectal toxicities and severity criteria are shown in Appendix II.
- *Biopsy failure rate*: The proportion of positive biopsy findings among patients without clinical or biochemical failure 2-2.5 years after completing study treatment.
- *Biochemical failure-free interval (BFFI)*: The elapsed time from study enrollment to first documented evidence of biochemical failure ($PSA \geq \text{nadir}+2$). In the absence of biochemical failure, follow-up time will be censored at the date of last documented biochemical failure-free status.
- *Biochemical failure (BF) rate*: The cumulative incidence of BF allowing for competing risk as needed.
- *Biochemical failure-free survival (BFFS)*: The elapsed time from study enrollment to first documented evidence of biochemical failure or death from any cause, whichever occurs first. In the absence of any event defining biochemical failure, follow-up time will be censored at the date of last documented biochemical failure-free status.
- *Failure-free interval (FFI)*: The elapsed time from study enrollment to first documented evidence of biochemical or clinical failure. Clinical failure is defined as local failure due to newly identified extension outside of the prostate after initial regression, or urinary obstructive symptoms with carcinoma found at TURP or regional/distant failure due to radiographic evidence metastasis (nodal or hematogenous spread). In the absence of any event defining failure, follow-up time will be censored at the date of last documented failure-free status.
- *Failure rate*: The cumulative incidence of biochemical or clinical failure allowing for competing risk as needed.

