10.0 MEASUREMENT OF TOXICITY

Acute proctitis and cystitis lasting for up to 4 months after completion of radiotherapy are accompaniments of radiotherapy for carcinoma of the prostate. The severity of these reactions is routinely evaluated during treatment and will be scored according to the criteria outlined in Appendix II. In our extensive experience, grade 3 or 4 acute toxicities are rare.

Delayed toxicities are usually related to urinary, rectal, and sexual function. The anticipated urinary and rectal toxicities and severity criteria are those shown in Appendix II. Other untoward clinical events will, however, also be documented.

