14.4 Interim Monitoring

We propose the following guidelines for the Sylvester Data and Safety monitoring Committee (DSMC) (see also Appendix III) in its review of accumulating data on toxicity and feasibility of study treatment. The proposed guidelines were developed using Bayesian methods, which can be applied at any stage of enrollment without advance specification of the number of interim analyses to be performed, or the number of patients evaluable for toxicity, or response, at the time such assessments are made.^{95,96}

Under the Bayesian method, we assign a prior probability (level of belief at the start of the trial) to a range of possible values for the true toxicity rate, and likewise for the true feasibility rate. As data on treated patients become available, each of these probability

Number of Patients With acute treatment Related Grade 3+ GI/GU Toxicity	Total Patients Evaluated	Observed Rate
2	3 to 6	≥33% (2 of 6)
3	7 of 11	≥27% (3 of 11)
4	12 to 16	≥25% (4 of 16)
7	17 to 25	≥25% (7 of 25)

distributions is revised and the resulting posterior probability becomes the basis for recommending either early termination or continuation of the study. In the sections that follow, we provide specific stopping guidelines based on posterior probabilities for monitoring toxicity and efficacy over the course of this trial. Underlying assumptions for the prior distributions are also presented.

Stopping rules for safety: The following early stopping guidelines, which are based on a Bayesian method, will be

applied to ensure safety of this Phase I trial. Safety monitoring will be based on the occurrence of treatment related (possible, probable, or definite) grade 3 or higher GI or GU toxicity occurring during study treatment or within 30 days of treatment completion. Early stopping (suspension and possibly termination) will be considered if there is evidence that the proportion of patients experiencing such toxicity exceeds 15%. Specifically, we suggest as a guideline for early termination a posterior probability of 80% or higher that the rate of grade 3 or higher GI/GU toxicity exceeds 15%. **Table 2** shows specific instances where this guideline is met, thus suggesting early termination due to evidence of excessive toxicity.

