As an additional safeguard, the first three patients enrolled on study will be observed for 30 days following treatment completion of the third patient before enrollment is continued (fourth patient). If two or three of the first three study patients have grade 3 or higher GI/GU toxicity within 30 days of treatment completion, enrollment will be suspended pending DSMC review. If none or one of the first three patients enrolled on study have grade 3 or higher GI/GU toxicity

within 30 days of treatment completion, enrollment will continue without restriction on the interval between successive enrollments.

Posterior probabilities used to derive the preceding table are calculated under a prior beta distribution with parameters $\beta_1 = 0.2$ and $\beta_2 = 1.8$, which corresponds to an expected rate of 15% based on prior information roughly equivalent to having studied 2 patients^{96,97}. Furthermore, this prior distribution assigns a small a priori chance (32%) to the possibility that the true rate of unacceptable toxicity is 15% or greater.

Table 3. Stopping Rules For Lack of Feasibility

Number of Patients ineligible For LEAD	Total Patients enrolled and completed CT simulation	Observed LEAD ineligibility rate
2	3	67%
3	4 to 6	≥50% (3 of 6)
4	7 to 10	≥40% (4 of 10)
5	11 to 13	≥38% (5 of 13)
6	14 to 17	≥35% (6 of 17)
9	18 to 25	≥35% (9 of 25)

Stopping rules for lack of feasibility

Similarly, for purposes of monitoring the feasibility of delivering LEAD RT, we consider the proportion of patients enrolled on study for whom it is not possible to deliver LEAD RT as determined from CT/MRI simulation and planning, referred to as the *LEAD ineligibility rate*. The LEAD treatment will not be delivered if the summed dose of LEAD and conventional treatment to critical structures exceeds tolerance. Early stopping due to infeasibility of the proposed study treatment will be considered if there is evidence that the rate of LEAD ineligibility exceeds

20%. Specifically, we suggest as a guideline for early termination a posterior probability of 90% or higher that the rate of unacceptable toxicity exceeds 20%. **Table 3** shows specific instances where this guideline is met, thus suggesting early termination due to early evidence of LEAD infeasibility.

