APPENDIX IV
DATA SUBMISSION SCHEDULE

FORM	TO BE COMPLETED
BASELINE	
Eligibility Checklist	Prior to registration
SCCC Protocol Enrollment Form	
Consent Forms Signed/dated	
On-study Form	Within 30 days of registration
DURING PROTOCOL THERAPY	
	Due every week for phase I studies, every cycle for phase II-IV studies
AFTER PROTOCOL THERAPY	
Off Treatment Form	Within 14 days of discontinuation/completion of protocol therapy
FOLLOW-UP SCHEDULE (for studies with long term follow-up)	
Follow-up Form	At during the last week of RT, and after RT at 6 weeks, 3 months, and every 6 months to 5.25 yr after RT.
Progression/Relapse	Within 4 weeks of knowledge of progression/relapse
Notice of Death Form	Within 4 weeks of knowledge of death
Subsequent Malignancy	Within 4 weeks of knowledge of another malignancy

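### No toxicity assessment is guaranteed in the 30 days after radiotherapy, so patient 4 can be enrolled before patient 3 has had any post-treatment assessment

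*Combined protocol and SAP*

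**What the plan says.** **The window.** The stopping rule in Section 14.4 counts treatment-related "grade 3 or higher GI or GU toxicity occurring during study treatment or within 30 days of treatment completion". Section 9.1 uses the same span for its broader grade 2+ definition of acute toxicity: events "occurring during treatment and within 30 days of completing treatment".

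**The run-in safeguard.** Section 14.4 adds that "the first three patients enrolled on study will be observed for 30 days following treatment completion of the third patient before enrollment is continued". With no or one qualifying event among the three, accrual then proceeds with no required interval between patients. Section 3.3, item 4, says only that "the monitor will inform the study team when the forth patient may be enrolled". It names no assessment or data source for that decision.

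**The assessments.** Section 5.2 schedules a toxicity evaluation every week during RT. After RT, Section 5.3 gives "evaluation of side effects at 6 weeks, 3 months, and then every 6 months for 5.25 years", with a tolerance of 2 weeks either way up to the 3-month visit. A footnote to Appendix I ties toxicity assessment to the scheduled history and physical visits. Appendix IV places the follow-up form in the last week of RT and then "after RT at 6 weeks, 3 months, and every 6 months to 5.25 yr after RT". An Off Treatment Form is due within 14 days of the end of therapy, but no examination is attached to it.

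**What can be recovered later.** Appendix I provides for interval history at follow-up visits, and Section 14.2 tabulates adverse events by time of onset.

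**The concern.** A rule with a 30-day post-treatment window needs a point at which someone establishes whether an event occurred in that window. The plan schedules none at or before day 30. The first visit after RT is nominally on day 42.

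Two decisions depend on this. The first is the release of patient 4, which the protocol presents as an extra safeguard. If the schedule is followed exactly, patient 3 can pass that point without having been assessed since the last week of RT. An event found at the 6-week visit cannot undo an enrollment already made. The second is Table 2, whose denominator is the number of patients evaluated. That term is not tied to a visit, so a patient could be counted as event-free before anyone has asked. Toxicity is part of the primary objective (Section 2.1), so these are the safety decisions that matter most in this trial.

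**Working it through.** The documents give no figure to reproduce here. The check sets dates side by side, taking *treatment completion* as the end of RT.

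**1. Post-RT visit against the window**
- Window closes: day 30 (Sections 9.1 and 14.4).
- First visit: 6 × 7 = day 42. With the 14-day tolerance (Section 5.3): 42 − 14 = day 28 to 42 + 14 = day 56, which is 29 permitted days.
- Permitted days at or before day 30: 28, 29 and 30, so 3 of 29. A visit on day 28 or 29 still leaves the end of the window uncovered.
- Days 1 to 27 contain no scheduled assessment.
- Gap between window close and visit: 42 − 30 = 12 days nominally, 56 − 30 = 26 days at most.

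**2. How much of the whole window is covered**
- RT lasts 7.5 weeks (Section 4.15): 7.5 × 7 = 52.5 days, assessed weekly.
- Whole window: 52.5 + 30 = 82.5 days.
- Covered by weekly assessment: 52.5 / 82.5 = 64%. No scheduled contact on days 1 to 27: 27 / 82.5 = 33%.

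**3. What happens to an event on days 1 to 30**
- If it is reported spontaneously, it is known in time for both decisions.
- If it is first mentioned at the 6-week visit, interval history and its onset date place it inside the window. Table 2 then counts it, late. The patient-4 decision has already been taken.

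**4. Illustration for the three-patient check only**

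The true rate of 30% and the share of events unknown at day 30 are assumptions; the documents give neither. The check trips with at least 2 events in 3 patients. With every event known, the probability is 3(0.3²)(0.7) + 0.3³ = 21.6%. If only patient 3's events can be unknown, and q is that patient's recorded rate, it is 0.3² + 2(0.3)(0.7)q = 0.09 + 0.42q:

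| Share unknown at day 30 | q | Patient 3 only | All three patients |
|---|---|---|---|
| 10% | 0.270 | 20.3% | 17.9% |
| 25% | 0.225 | 18.5% | 12.9% |
| 50% | 0.150 | 15.3% | 6.1% |

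This shows the direction of the effect. It does not measure its size in this trial.

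**The case against.** **Most of the window is watched.** A reader might infer that the safety rule rests on time in which nobody is assessed. The documents do not support that. The rule includes the RT period, which is assessed weekly. Adverse-event reporting is continuous, and Appendix III gives the monitoring committee ongoing review of adverse events.

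**Table 2 events are delayed, not lost.** One could model permanent loss: if a true 20% rate were recorded as 15%, the chance of ever crossing the printed Table 2 boundaries would fall from 55.0% to 34.9%. But that assumes a quarter of all events (5 of 20 points) are never counted. Interval history and onset dating contradict this, so the figures are not evidence of size. Nor does Section 14.4 say that a patient becomes evaluated on day 30; waiting for the visit is already allowed. What remains is that it is not required.

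**Section 10 concerns persistence.** It says "Acute proctitis and cystitis lasting for up to 4 months after completion of radiotherapy are accompaniments of radiotherapy". A reader might conclude that the 30-day limit excludes much acute toxicity. The sentence describes how long reactions last, not when they begin. A reaction that meets the criterion by day 30 and persists is counted.

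**Release permits enrollment, not irradiation.** Marker placement may take up to 4 weeks (Section 4.15), and MRI simulation follows at least 1 week later (Section 4.6). Patient 4's LEAD fraction could not come before about day 30 + 7 = 37, and with marker placement at 4 weeks not before 30 + 28 + 7 = 65. Patient 3's 6-week visit may well come first, Table 2 still stops at 2 events in 3 to 6 patients, and patients 1 and 2 may already have had their visits. This reduces the exposure but does not remove it: day 37 precedes both day 42 and day 56, and Section 14.4 places the safeguard at enrollment.

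**Conclusion.** The point holds in a limited form. No scheduled toxicity assessment is guaranteed between the last week of RT and day 30, so the post-treatment part of the safety window depends on spontaneous reports or later recall. The consequence is clearest for patient 4, whose enrollment can precede any post-RT assessment of patient 3, nominally by 12 days and at most by 26. For Table 2 the effect is mainly delay, with the added risk that a patient is counted as event-free too early.

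This rests on the schedule as written and on reading *treatment completion* as the end of RT. Sections 9.1 and 14.4 do not define the term, and for biopsy timing Section 8.0 uses the later of RT and androgen deprivation. The number of events that would be unknown at day 30 cannot be derived from the documents. The change is worth making as an inexpensive safety improvement; it is not a condition for the trial's validity.

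**What to change.** Keep the 30-day onset window and the 15% threshold.

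- **Section 14.4, Table 2:** state that a patient without an event counts as evaluated only when the first post-RT toxicity assessment at or after day 30 is complete, with onset dates recorded. This is normally the existing 6-week visit. A patient with a qualifying event counts at once.
- **Section 14.4, run-in, and Section 3.3, item 4:** state that patient 4 is released only after that assessment of the third patient.
- **Sections 9.1 and 14.4:** state that *treatment completion* means the end of RT.

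Extending the acute endpoint itself to the 6-week visit is not advised. The window would then vary from 28 to 56 days between patients, and the 15% threshold was set for 30 days.

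**Cost.** Protocol wording and a run-in hold that is nominally 12 days longer, at most 26. No extra visit is needed, provided the 6-week visit is booked on day 30 or later within its existing tolerance. Counting events at once while event-free patients wait makes the interim rate look slightly high for a time, which errs toward caution.

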- D. All patients may receive 4-6 months (+/- 2 months) of ADT at the discretion of the treating physician, if the patient agrees. Patients with Gleason score ≥8 must be offered long term androgen deprivation therapy (ADT) and refuse such treatment because only 4-6 months (+/- 2 months) (short term ADT) is permitted (not required) on this protocol. The ADT is recommended to begin after fiducial marker placement; however, is permitted to have been started up two months prior to the signing of consent.
- E. PSA ≤30 ng/mL within 3 months of enrollment.
- F. No previous pelvic radiotherapy.
- G. No previous history of radical/total prostatectomy (suprapubic prostatectomy is acceptable).
- H. No concurrent, active malignancy, other than non-metastatic skin cancer or early stage chronic lymphocytic leukemia (well-differentiated small cell lymphocytic lymphoma). If a prior malignancy is in remission for ≥ 5 years then the patient is eligible.
- I. Identifiable multiparametric MRI-defined tumor lesion or lesions, that total in volume <33% of the prostate.
- J. Ability to understand and the willingness to sign a written informed consent document.
- K. Zubrod performance status <2.

- L. Patients must agree to fill out the psychosocial questionnaires.
- M. Bone scan negative if PSA >15 ng/mL or Gleason \geq 8 disease. A questionable bone scan is acceptable if plain x-rays and/or MRI are negative for metastasis.
- N. Serum testosterone is within 40% of normal assay limits (e.g., $x=0.4$ *lower assay limit and $x=0.4$ *upper assay limit + upper assay limit), taken within 4 months of enrollment. Patients who have been started on ADT prior to signing consent are not required to have a serum testosterone at this level prior to signing consent; but, a serum testosterone prior to fiducial marker placement is recommended.
- O. Serum liver function tests (LFTs) are taken within 3 months of enrollment.
- P. Complete blood counts are taken within 3 months of enrollment.
- Q. Age \geq 35 and \leq 85 years.

2. After Enrollment and Prior to Treatment

- A. Transrectal research prostate biopsies and gold seed fiducial marker placement:

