 - a. The pre-RT prostate biopsy is optional for the patient, while the fiducial marker placement is not. For the prostate biopsies, up to a maximum of 14 cores will be taken prior to fiducial marker placement. The number of biopsy cores taken would be up to the discretion of the urologist in conjunction with the team, and does not have to be defined prior to biopsy if the patient agrees to undergo the procedure.
 - b. Ultrasound-guidance is standard for prostate biopsies. The Eigen Artemis® system may be used to fine tune the biopsy locations within the prostate using software to fuse the multiparametric MRI to the ultrasound in real time as the ultrasound is acquiring the images. In addition, these biopsies may be obtained on an MRI directly using established techniques.
 - c. 3-4 gold seeds placed in prostate (4 preferred)
- B. MRI-simulation: Limited study without contrast at least 1 week after gold fiducial placement.
- C. CT-simulation and planning.

3. Treatment Technique

- A. LEAD RT: 12-14 Gy dose pipes on day 1.

The LEAD dose distribution may be planned and delivered by the Cyberknife, an image-guided robotic SBRT system, or on a standard LINAC,. The LEAD RT dose plan will involve the placement of 1 to 3 dose pipes of 7-12 mm diameter the length of the multiparametric MRI GTV volume; but, may extend up to 6 mm above and 6 mm below the GTV. The GTV will include the multiparametric MRI-defined suspicious lesions defined by either early phase contrast enhancing lesion on dynamic contrast enhanced (DCE)-MRI or water restriction on the Apparent Diffusion Coefficient (ADC) maps, considered with the abnormality on T2-weighted imaging. For anterior lesions in the transition zone an abnormality based on only DCE-MRI is not enough and must be accompanied by, restricted water motion on diffusion weighted imaging (DWI) via an ADC point value of <1000 and/or increased choline + creatinine relative to citrate (\geq 0.9 ratio) on MR spectroscopy (MRS). The LEAD RT region(s) will be centered in the GTV region(s), but may extend out of the GTV to avoid being too close to the vital structures (rectum, urethra, bladder or penile bulb. The LEAD regions should be positioned \geq 2 mm from the vital structures to avoid excessive dose to these structures. Up to three dose pipes spaced by approximately 1.5 – 2.0 cm may be used, with no more than two per side of the prostate. The LEAD RT dose pipes will be covered by 12-14 Gy with a maximum of 20 Gy. The

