3.3.1 Cancellation Guidelines

If a patient does not receive protocol therapy, the patient may withdraw. Patients who are enrolled on study but not treated with the LEAD component of the protocol will be excluded from all analyses.

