11.2.1 Determination of Reporting Requirements

Reporting requirements may include the following considerations:

- 1) whether the patient has received an investigational or commercial agent;

2) the characteristics of the adverse event including the grade (severity), the relationship to the study therapy (attribution), and the prior experience (expectedness) of the adverse event;

3) the Phase (1, 2, or 3) of the trial; and 4) whether or not hospitalization or prolongation of hospitalization was associated with the event.

11.2.2 Steps to determine if an adverse event is to be reported in an expedited manner:

Step 1: Identify the type of event using the NCI Common Toxicity Criteria (CTC).

The CTC provides descriptive terminology and a grading scale for each adverse event listed. A copy of the CTC can be downloaded from the CTEP home page (<http://ctep.cancer.gov>). Additionally, if assistance is needed, the NCI has an Index to the CTC that provides help for classifying and locating terms. All appropriate treatment locations should have access to a copy of the CTC.

Step 2: Grade the event using the NCI CTC.

Step 3: Determine whether the adverse event is related to the protocol therapy (investigational or commercial).

Attribution categories are as follows: Unrelated, Unlikely, Possible, Probable, and Definite.

Step 4: Determine the prior experience of the adverse event.

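### Harm from seed placement and the research biopsies is misplaced in the toxicity tables: before LEAD it fits neither acute nor late, and at 2-2.5 years it falls into late toxicity

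*Combined protocol and SAP*

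**What the plan says.** **Before radiotherapy.** The Schema puts seed placement and the research biopsy under the heading "After Enrollment and Prior to Treatment". The seeds are mandatory and the biopsy is optional: "For the prostate biopsies, up to a maximum of 14 cores will be taken prior to fiducial marker placement". Section 4.15 schedules both within 4 weeks of enrollment.

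**Toxicity definitions.** Section 9.1 defines acute toxicity as "Grade 2 or higher treatment-related acute GU/GI toxicity occurring during treatment and within 30 days of completing treatment". For late toxicity it says only "Delayed toxicities are usually related to urinary, rectal, and sexual function" and points to Appendix II for severity. It gives no start, no end and no required relation to treatment.

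**Tabulation.** Section 14.2 promises lists and tables of every adverse event, with grade, attribution and timing relative to treatment. It then splits them into acute and late as in 9.1.

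**Stopping rule.** Section 14.4 states "Safety monitoring will be based on the occurrence of treatment related (possible, probable, or definite") events, namely "grade 3 or higher GI or GU toxicity occurring during study treatment or within 30 days of treatment completion".

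**Exclusion.** Section 3.3.1: "Patients who are enrolled on study but not treated with the LEAD component of the protocol will be excluded from all analyses".

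**Later biopsy.** Section 8.0 plans a research biopsy for all men at 2-2.5 years, with 12 to 14 cores preferred, unless it is contraindicated or refused.

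**Attribution.** Step 3 of section 11.2.2 reads "Determine whether the adverse event is related to the protocol therapy (investigational or commercial"). Section 11.1.1 is wider and applies the five-level attribution scale to a treatment or a procedure.

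**The concern.** The protocol adds invasive procedures of its own, and the safety tables have no place for the harm they cause. The error runs in opposite directions at the two ends of the trial.

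Before LEAD, a procedure complication has no table to go into. One serious enough to prevent LEAD takes the man out of the safety report altogether. After the 2-2.5 year biopsy, bleeding, retention or infection enters the late urinary and rectal profile as if it might be an effect of the radiation.

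Toxicity is half of the primary objective in section 2.1, and there are only 25 men. One or two misplaced events would change what the report says about LEAD.

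**Working it through.** The core of the check is a comparison of passages. The plan states no complication rate, so there is no figure of its own to reproduce on this point.

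**1. A complication between seed placement or biopsy and LEAD**

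- Acute table (9.1): the window opens with treatment. The Schema puts these procedures before treatment, and section 6.1 names radiation as the study agent. On that reading the event falls outside.
- Late table (9.1): no start time is stated, but a delayed toxicity of treatment cannot come before treatment. The event falls outside.
- Stopping rule (14.4): same window as the acute definition, plus relation to treatment. The event falls outside.
- Scheduled detection: Appendix I assesses toxicity at scheduled history and physical visits. These fall before RT and then weekly during RT, with no visit tied to the days after the procedure.
- Recording: the event should still be captured as an adverse event. Section 11.1.1 covers procedures, section 13.0 asks for data on all registered patients, section 14.2 lists all adverse events, and Appendix III has the DSMC review adverse-event data.

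**2. The same complication when it prevents LEAD**

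Section 3.3.1 then applies and makes no exception for safety. Table 3 does not pick the man up either if he leaves before planning, because it counts men who completed CT simulation. He can be recorded and still be in no reported analysis.

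**3. A complication of the 2-2.5 year biopsy**

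The acute window has closed. Late toxicity has no attribution condition, so a urinary or rectal event is late toxicity by timing alone.

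**4. Attribution wording**

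Section 11.1.1 allows attribution to a procedure. Step 3 of 11.2.2 asks about protocol therapy, and 11.1.5 defines relatedness in terms of a drug. Staff following Step 3 have no stated way to mark an event as due to the biopsy.

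**5. Size before RT**

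Inputs: n = 25 (section 14.1). Assumed grade 3 or higher complication rate per man, r = 1% to 5%. This is an assumption, since the documents give none.

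P(at least one event) = 1 - (1 - r)^25

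- r = 0.01: 1 - 0.99^25 = 0.222
- r = 0.05: 1 - 0.95^25 = 0.723

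These are upper figures for each r. They apply the rate to all 25 men, although the biopsy may be refused and enrollment may stop early.

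**6. Should procedure events be added to the Table 2 count?**

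Take a true radiotherapy toxicity rate of 10% and independent procedure harm h. The combined rate is 1 - (1 - 0.10)(1 - h), which is 0.109 for h = 1% and 0.145 for h = 5%. Using the printed Table 2 boundaries, checked after every man from the third, the exact probability of meeting the guideline is:

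| Procedure harm counted | Combined rate | P(guideline met) |
|---|---|---|
| none | 0.100 | 16.5% |
| 1% | 0.109 | 19.4% |
| 5% | 0.145 | 32.9% |

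Adding these events would make the rule fire more often for harm that LEAD did not cause. That argues for listing them separately.

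**The case against.** The strongest reply is that the plan already has general safety nets. Every adverse event is listed with attribution and onset (14.2), the definition covers procedures (11.1.1), and the DSMC sees adverse-event data as they accrue (Appendix III). A careful analyst could find a bleed dated days after the biopsy, and late toxicity is descriptive, with no threshold to distort. This stands in part. A reader might infer that procedural harm is counted nowhere, or that attribution to a procedure is never asked. Neither is supported: the gap is in the defined toxicity tables and in 3.3.1, not in raw capture. But listing an event does not place it in a table, no rule says how the later bleed is to be separated, and the listing does not override 3.3.1.

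A second reply is that the stopping rule is meant for treatment toxicity. That is right. A reader might take the rule itself to be defective, but limiting it to treatment-related events is a sound choice.

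A third reply is that nothing states when study treatment starts. Section 4.0, titled as the treatment plan, includes the biopsy and seeds (4.3), and 4.15 opens with them. The first-three-patients check in 14.4 gives no start and no attribution condition, and Table 2 accepts a possible relation, so an event persisting into RT could count. This stands: a start at RT is an inference from the Schema and 6.1. The ambiguity is itself a reason to state the start.

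Finally, the seeds serve targeting (4.6), so they cannot be described as research without a treatment purpose. The 3.3.1 route also needs an event that actually prevents LEAD, which will be less common than the events sized above.

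**Conclusion.** The point holds in a limited form. Followed as written, 9.1 and 14.2 give pre-LEAD procedure harm no place in the acute or late tables, 3.3.1 can remove the affected man from safety reporting, and harm from the 2-2.5 year biopsy enters late toxicity by timing.

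For pre-RT harm, the chance of at least one grade 3 or higher event in 25 men is at most 22% to 72%. This rests wholly on the assumed 1% to 5% rate. The documents do not allow an estimate of how many such men would miss LEAD, or of how many late events the later biopsy would add.

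Two larger claims of size are tempting and should not be made. Pooling the pre-RT and later biopsies into one probability mixes events left out with events wrongly included. Setting one late bleed in 25 men against the 8-year rectal bleeding risk quoted in 1.5 compares a crude fraction with a long-term risk from another series, which section 14 does not use as a comparator.

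The change is worth making because toxicity is a primary objective and the correction is nearly free.

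**What to change.** 1. **Section 3.3.1.** State that the exclusion does not apply to safety reporting. Report adverse events from seed placement or biopsy onward for every man who had the procedure, whether or not LEAD was given.
2. **Sections 9.1 and 14.2.** Add a study-procedure category covering the time from seed placement or biopsy to LEAD, and the 30 days after the 2-2.5 year biopsy. Align Step 3 of 11.2.2 with 11.1.1, so that relation to a study procedure can be recorded.
3. **Late toxicity.** Show late GU/GI toxicity with and without events in the 30 days after the protocol biopsy.
4. **Section 14.4.** State when study treatment starts. Keep the Table 2 count limited to treatment-related toxicity, and list grade 3 or higher procedure events for the DSMC beside it.

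The cost is one attribution field and two extra tables. No visits, procedures or patients are added.
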